Evaluation of an Artificial Intelligence-Assisted, Image-Based Dietary Assessment Tool in the Framingham Heart Study

NCT06455111

[name]

[contact]

Statistical Analysis Plan pages 3-4

Evaluation of an Artificial Intelligence-Assisted, Image-Based Dietary Assessment Tool in the Framingham Heart Study

Background: Assessment of dietary intake in large, free-living populations is inherently challenging due to the complex nature of human diet. Advancements in traditional methods of dietary assessment (i.e., web-based dietary recalls or records) have aimed at improving data accuracy while reducing participant burden. Further utilizing food recognition technologies to capture real-time food intake may aid in overcoming limitations of existing methods. Keenoa[□], an artificial intelligence-enhanced, image-assisted tool, is a newly designed mobile application that may facilitate collection of dietary data.

Aims: Primarily, we will assess acceptability and usability of Keenoa compared with the traditional, web-based Automatic Self-Administered 24-Hour (ASA24) Dietary Assessment Tool in the Framingham Heart Study Third Generation-based cohorts at examination 4. We will also determine the proportion of participants who complete all three days of dietary assessment with energy intake >600 kcal, either through Keenoa or ASA24.

Methods: With a randomized block design, this study will take place as part of the Framingham Heart Study (FHS) glucose study (R01 DK129305). We currently ask participants from the Third Generation-based cohorts, at their fourth examination, to wear Dexcom G6 Pro continuous glucose monitor on either their arm or abdomen for a duration of at least 4 days. During this time, we request participants to complete 3 consecutive days of dietary record through ASA24. For the purpose of this trial, we will randomize the dietary assessment tool weekly between ASA24 and Keenoa, therefore, depending on the week of administration, participants are randomized to either a 3-day dietary record via ASA24 or a 3-day dietary record through Keenoa. This trial will last a total of 6 weeks.

Background and Rationale

Assessment of dietary intake in large, free-living populations is inherently challenging due to the complex nature of human diet.¹ In epidemiological studies, methods of self-reported dietary assessment include food frequency questionnaires, multiple 24-hour dietary recalls and food records.¹ Although each instrument has a unique set of limitations, common concerns primarily revolve around issues of measurement error, high respondent burden, and high administrative cost.² Utilizing technology-based dietary assessment methods present opportunities for improving data accuracy while reducing the financial burdens associated with having trained dietary interviewers.³ With advances in technology, web-based dietary assessment tools, such as the Automated Self-Administered 24-Hour (ASA24) dietary recall or record, have been developed, extensively validated, and used in population-based studies.⁴ In recent years, image-based or image-assisted food recognition smartphone applications (apps) have also entered the nutrition science research space, with evidence suggesting that incorporating these apps may reduce energy underreporting and enhance the validity of self-reported dietary intake.⁵⁻⁸

Keenoa™ is an artificial intelligence-enhanced, image-assisted dietary assessment tool that has been originally designed to facilitate dietary data collection for dietitians and researchers.⁹ Serving as a visual food diary, individuals can upload a picture of their meal, choose the food items eaten using a preselected food list available by the app, and confirm the portion size with the presented visual aids. Two recent trials have aimed to evaluate the validity and usability of Keenoa™ against common methods of dietary assessment.^{10,11} In a randomized controlled trial of 72 Canadian adults, Keenoa™ performed better on analyzing group-level micronutrient intake relative to individual-level intake, suggesting its potential appropriateness for assessing dietary intake of the general population.⁹ In the same study, a greater proportion of participants preferred using Keenoa™ over a traditional pen-and-paper method (34.2% vs. 9.6%).⁹ Another randomized crossover trial with 136 participants showed that Keenoa™ has moderate to strong agreement, when compared against ASA24 recalls, in analyzing energy, macronutrient, and the majority of micronutrient intakes in both healthy adults and those with type 2 diabetes mellitus (T2DM).¹¹ In addition to Keenoa™, several image-based or image-assisted dietary assessment apps have been developed for research purposes.¹² With distinct interfaces, some of these apps, such as the mobile food record (used in All of Us Precision Nutrition study), require uploading pictures from specific distance or angle of the food to ensure precise portion size estimation, which in turn may impose burden on participants. Therefore, selecting proper technology-based instrument relies upon different factors including available resources, study objectives, study population,

etc.,¹² and we chose to assess the acceptability and feasibility of KeenoaTM in order to evaluate dietary habits in the Framingham Heart Study (FHS).

Specific Aims

We will assess the following aims in the FHS Third Generation-based cohort exam 4.

Aim 1: Evaluate acceptability of the Diet Tracking Smartphone Application KeenoaTM, and compare it to that of ASA24 diet records among older adults. We hypothesize that dietary assessment through KeenoaTM is more acceptable than ASA24, using quantitative satisfaction scale (0-5).

Aim 2: Determine the response rates; defined as the proportion of participants who complete all three days of diet assessments with energy intake >600 kcal, either through KeenoaTM or ASA24. We hypothesize that Keenoa will have higher response rate for those completing 3-day diet records.

Methods

We will conduct a randomized block trial, recruiting participants from the Third Generation-based cohorts, at their fourth examination. For the purpose of this trial, we will randomize the dietary assessment tool weekly between ASA24 and KeenoaTM, therefore, depending on the week of administration, participants are randomized to either a 3-day dietary record via ASA24 or KeenoaTM. Refer to **Figure 1** for complete description of enrollment process.

During the weeks when KeenoaTM is administered: we will ask the participants if they have a smartphone. If not, individuals will not be eligible to participate in the trial, but they can still complete ASA24 dietary records, allowing their dietary information be collected for the FHS Glucose Monitoring Study. Then we will ask participants if they have a Google Play ID (for Android users) or Apple ID (for IOS users). If yes, our research technician at FHS center will help participants in setting up KeenoaTM. If not, we will provide participants with at home instruction protocol.

Statistical Analysis Plan

Power calculation: We estimate that we will require ~50 participants per group to complete aims 1 and 2.

Over the first 8 months of the current exam, we have had a response rate of 62.1% of participants completing 3 days of diet record using ASA24. We estimate that KeenoaTM would have an 80% response rate among our participants, therefore, considering alpha=.05, and 80% power, the sample size required is 50 participants per group.

Aim 1 analysis:

We will use chi-square to evaluate whether the average satisfaction rate (out of 5) of the two instruments (Keenoa vs. ASA24) is statistically significantly different.

Aim 2 analysis:

We will use chi-square to evaluate whether the response rates, defined as the percentage who completed 3 days of dietary assessment with energy intake >600 kcal, from the two instruments (Keenoa vs. ASA24) are statistically significantly different.

We will generate a summary of participant characteristics using descriptive statistics.

References:

1. Willett W. *Nutritional epidemiology*. Oxford university press; 2012.

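### One draw sets the tool for a whole week, so the tool can be known before a person enters the trial, and entry or refusal can depend on it

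*Combined protocol and SAP*

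**What the plan says.** Methods makes the calendar week the unit of allocation: "we will randomize the dietary assessment tool weekly between ASA24 and KeenoaTM". A participant's tool then follows from the week attended: "depending on the week of administration, participants are randomized to either a 3-day dietary record via ASA24 or KeenoaTM". The Methods paragraph of the opening summary gives the number of draws: "This trial will last a total of 6 weeks". The Statistical Analysis Plan gives the size: "We estimate that we will require ~50 participants per group to complete aims 1 and 2".

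The smartphone question is described only for weeks whose tool is already set: "During the weeks when KeenoaTM is administered: we will ask the participants if they have a smartphone". Of those without a phone it says: "individuals will not be eligible to participate in the trial, but they can still complete ASA24 dietary records".

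The design is labelled a randomised block trial, but no block size, sequence or ratio of weeks is given. The readable text also does not say who holds the week list, when a week's tool is revealed, whether people agree to keep a record before they hear which tool it is, or whether refusals are logged. Methods refers to Figure 1 for the full enrolment process, and that figure is not in the copy reviewed.

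**The concern.** With one draw per week, everyone seen in that week gets the same tool. Once staff know the tool for the week, they know it for each later person in that week before that person is invited. People can also hear the tool before deciding whether to take part.

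This is foreknowledge of allocation. It differs from two neighbouring issues. Asking about smartphones in every week would equalise one exclusion, and allowing for the correlation of participants within a week would correct the standard error. Neither stops entry from depending on the tool.

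The Aim 2 endpoint makes this matter. Willingness to use a tool is plausibly tied to finishing a 3-day record with it. If reluctant people leave one arm before they are counted, that arm's completion rate moves without any effect of the tool. The Aim 1 satisfaction comparison is exposed in the same way. The planned chi-square tests compare whoever entered, so they can neither detect nor correct this.

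**Working it through.** **Share of allocations knowable in advance.** The documents state no figure for this, so there is none to reproduce. Inputs: 6 weeks (opening summary) and about 50 per group, so N is about 100 (Statistical Analysis Plan). If staff learn a week's tool only from its first participant, the share known is (N − weeks that could not be foreseen)/N.

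- Weeks drawn independently: (100 − 6)/100 = 94%.
- Three weeks of each tool in one block: on average 1.5 weeks are forced by the earlier ones, so (100 − 4.5)/100 = 95.5%.
- Blocks of two weeks: 3 weeks are forced, so (100 − 3)/100 = 97%.
- Tool known at the start of each week: 100%.

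The result depends on N: 54/60 = 90% for 60 participants and 194/200 = 97% for 200.

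**What selective refusal could do.** All of the following are assumptions, except the 62.1% and the 50 per group:

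- The true completion rate is 62.1% with both tools. This is the ASA24 rate in the Statistical Analysis Plan: "we have had a response rate of 62.1% of participants completing 3 days of diet record using ASA24".
- A fraction r of those approached in Keenoa weeks refuse on hearing the tool, and nobody refuses in ASA24 weeks.
- Refusers leave the denominator.
- Refusers would have completed at rate c.

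The apparent Keenoa rate is (0.621 − r × c)/(1 − r). Rejection is the exact probability that a two-sided Pearson chi-square test at 0.05, with 50 per group, declares a difference. Participants are treated as independent.

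| r | c | Apparent Keenoa rate | Shift (points) | Rejection |
|---|---|---|---|---|
| 0 | – | 62.1% | 0 | 5.1% |
| 10% | 0 | 0.621/0.90 = 69.0% | +6.9 | 11.1% |
| 10% | 31% (about half of 62.1%) | (0.621 − 0.031)/0.90 = 65.6% | +3.5 | 6.5% |
| 10% | 62.1% (average) | (0.621 − 0.0621)/0.90 = 62.1% | 0 | 5.1% |
| 10% | 100% | (0.621 − 0.10)/0.90 = 57.9% | −4.2 | 7.4% |
| 15% | 0 | 0.621/0.85 = 73.1% | +11.0 | 21.3% |

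For scale, the plan's assumed effect is 80 − 62.1 = 17.9 points, so a 6.9-point shift is 6.9/17.9 = 39% of it.

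**Effect of the denominator.** If the 10% who refuse are kept and counted as non-responders, the c = 0 case gives 0.90 × 69.0% + 0.10 × 0 = 62.1%, and the inflation disappears.

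**The case against.** **Figure 1 may already answer this.** The order of invitation, agreement, screening and disclosure is what an enrolment figure would show, and it was not seen. This stands, and it makes the part about a missing agreement step conditional. It does not undo the weekly draw, which the text states plainly.

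**The 94% is not in the documents.** This also stands. A reader might infer that staff do know 94% of allocations. The figure needs about 100 participants, independently drawn weeks and disclosure at each week's first participant, and no rule for disclosure is given. The wording on Keenoa weeks suggests that the tool is known before screening starts, which would put the share near 100%.

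**The bias depends on a denominator rule that the plan does not give.** Aim 2 defines the response rate among participants without saying how those who refuse on hearing the tool are counted. Only people without a smartphone are expressly excluded. The objection is correct, and it is why the fix must settle the denominator.

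**The direction is unknown.** A reader might infer inflation in favour of Keenoa. That follows only if the people lost are worse completers than average. Average completers give no shift, and certain completers shift the result against Keenoa.

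**Staff steering is conjecture.** These are cohort members attending a scheduled examination, and nothing shows that staff choose visit dates or invite selectively. That is fair. Refusal by participants after hearing the tool remains possible without any steering.

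**Weekly allocation may be practical.** Technicians help to set up Keenoa, and running one tool at a time is simpler. The documents do not give this as the reason, but it is plausible, so per-participant allocation should not be the only remedy offered.

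**Conclusion.** The point holds in a limited form. Weekly allocation makes the tool knowable in advance for at least about 94% and up to 100% of participants, assuming about 100 participants over 6 weeks. The readable text shows nothing that separates agreement from disclosure of the tool, subject to Figure 1. Entry or refusal can therefore depend on the tool, and this can bias both comparisons in either direction.

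The documents do not show that selection will occur, how large it would be, or which tool it would favour. Under the stated assumptions, 10% loss in Keenoa weeks puts the apparent Keenoa rate between 57.9% and 69.0%, with rejection between 5.1% and 11.1% when there is no true difference. The upper end of the rate assumes that everyone lost was a certain non-completer. The bias in satisfaction cannot be quantified from the documents. The change should be made because the exposure is unmeasured and the basic remedy is cheap.

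**What to change.** First check Figure 1. If it already contains a tool-neutral agreement step, state that step in Methods. Otherwise amend Methods as follows:

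1. In every week, before the tool is disclosed, ask the same eligibility questions, including smartphone ownership.
2. Obtain agreement to keep a 3-day record on a script that does not name the tool.
3. Log everyone who agrees, by week.
4. Analyse all of them under that week's tool. For Aim 2, count those who then decline as non-responders.

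The cost is a change in the order of questions, a short log and a brief amendment. Two limits remain. Staff may still know the week's tool, so this reduces foreknowledge by staff without removing it. People who decline after disclosure will have no satisfaction score, so their number should be reported by tool beside the Aim 1 result.

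Where visit staff can run either tool on any day, a concealed per-participant draw, opened only after steps 1 and 2, is the stronger option. Its cost is a randomisation module and having both tools ready daily.

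### The smartphone screen and exclusion are described only for Keenoa weeks, so the two arms can differ in eligibility and both comparisons can be biased

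*Combined protocol and SAP*

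**What the plan says.** All of the following is in the combined protocol and SAP.

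- **Allocation (Methods).** "we will randomize the dietary assessment tool weekly between ASA24 and KeenoaTM". The tool is therefore fixed by the calendar week before an individual participant is screened.
- **Screen (Methods).** "During the weeks when KeenoaTM is administered: we will ask the participants if they have a smartphone". The consequence for non-owners follows directly: "If not, individuals will not be eligible to participate in the trial, but they can still complete ASA24 dietary records". Those records serve the parent glucose study.
- **ASA24 weeks (Methods).** The text describes no smartphone question and no exclusion.
- **Full enrollment process (Methods).** The reader is sent to Figure 1 "for complete description of enrollment process". The figure is not reproduced in the text available for this review.
- **Outcomes (Specific Aims).** Aim 1 compares a 0–5 satisfaction score between the tools. Aim 2 compares "the proportion of participants who complete all three days of diet assessments with energy intake >600 kcal".
- **Analysis (Statistical Analysis Plan).** For Aim 2, "We will use chi-square to evaluate whether the response rates" differ between the instruments. Aim 1 is also assigned a chi-square test. Neither analysis mentions restriction to, or adjustment for, smartphone ownership.

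**The concern.** An exclusion applied after allocation and in one arm only is not protected by randomization. A non-owner who attends in a Keenoa week is out of the trial. The same person attending in an ASA24 week is, on the visible text, counted in the ASA24 arm. The comparison then mixes the effect of the tool with the effect of who was allowed into each arm.

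ASA24 is itself web-based, and Aim 1 refers to older adults, so people without a smartphone could plausibly complete or rate it differently from owners. The documents do not establish that they do. If they complete ASA24 less often, Aim 2 is biased towards Keenoa, which is the hypothesized direction. If they complete it more often, the bias favours ASA24. For Aim 1 the documents do not allow a direction or size to be given.

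The planning figures raise the same question. The 62.1% ASA24 rate comes from exam participants with no stated owner restriction, while the 80% Keenoa rate would be realized among owners only.

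**Working it through.** **The plan's own figure.** The SAP gives 50 per group for 62.1% against 80%, alpha .05, 80% power. With the usual two-proportion formula (pooled variance under the null, two-sided):

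n = [1.960·√(2 × .7105 × .2895) + 0.842·√(.621 × .379 + .80 × .20)]² / .179² = [1.257 + 0.529]² / .0320 ≈ 100 per group.

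The stated 50 does not reproduce (one-sided gives 79), and 50 per group gives about 50.5% two-sided power. That is a separate matter. The point made here does not depend on it, and 50 per group is used below because it is the planned size.

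**Inputs from the documents.** ASA24 completion 62.1%; planned difference 80 − 62.1 = 17.9 points; 50 per group; alpha .05 (sidedness not stated; two-sided used here).

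**Inputs assumed.** Let m be the share of ASA24-week participants without a smartphone and g the owner-minus-non-owner gap in ASA24 completion. Neither is in the documents. The 62.1% is taken as the rate for owners and non-owners together.

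**Shift.** If owners complete ASA24 at rate p, the mixed arm completes at (1 − m)p + m(p − g) = p − mg. Setting this to .621 gives p = .621 + mg. With no true difference between the tools among owners, the owners-only Keenoa arm also has rate p. The spurious difference is therefore m × g.

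**Rejection rate with no tool effect.** Exact enumeration of two independent binomials of size 50, ASA24 at .621 and Keenoa at .621 + mg:

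| m | g (points) | Shift m × g (points) | Share of 17.9 | Rejection, uncorrected | Rejection, continuity-corrected |
|---|---|---|---|---|---|
| any | 0 | 0 | 0% | 5.1% | 3.1% |
| 5% | 10 | 0.5 | 2.8% | 5.1% | 3.1% |
| 5% | 20 | 1.0 | 5.6% | 5.2% | 3.2% |
| 10% | 30 | 3.0 | 16.8% | 6.1% | 3.9% |
| 20% | 40 | 8.0 | 44.7% | 13.3% | 9.4% |
| 5% | −20 | −1.0 | 5.6%, towards ASA24 | 5.2% | 3.2% |
| 20% | −20 | −4.0 | 22.3%, towards ASA24 | 7.2% | 4.7% |

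The total rate understates the directional effect. False findings in favour of Keenoa (uncorrected) rise from 2.5% with no shift to 5.0% in the 10%/30-point case and 13.0% in the 20%/40-point case.

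**Which step causes the asymmetry.** Only the smartphone question does. Participants without a Google Play or Apple ID are not excluded; they receive instructions for set-up at home.

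**The case against.** The strongest reply is that the Methods defer to Figure 1 for the full process, and a figure that cannot be seen here cannot be called missing from the plan. The paragraph in question may only list what staff do in Keenoa weeks. The exclusion is also worded at the level of the trial, not the arm. This stands as a limit on certainty: Figure 1 may show a common screen. It does not remove the point, because a trial-wide rule needs a step that identifies non-owners in ASA24 weeks, and the text gives none.

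Second, the size is assumed throughout. Smaller gaps or shares make it negligible: a 5% share with a 10-point gap shifts the result by half a point. The largest case needs non-owners completing at about 30% against 70% for owners. That is correct.

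Third, the rejection rates treat participants as independent, although the tool is allocated by week over six weeks. They therefore describe a simplified model, and any correlation within weeks would change the absolute rates. The shift m × g does not rest on that assumption.

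Fourth, ownership might be recoverable from data held by the parent cohort. The documents neither say so nor rule it out. It is safer to say that no such data are described than that correction would be impossible.

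Fifth, comparing owners with owners may shrink the expected difference. This is a fair point about cost and is taken up under the fix.

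**Conclusion.** The concern holds. On the visible text, a smartphone criterion is applied after allocation and in the Keenoa arm only, and the planned tests do not account for it. For Aim 2 the bias is m × g: zero if non-owners respond like owners, about 3 points in a middle case (10% share, 30-point gap), and 8 points, or 45% of the planned difference, only if both assumptions are at their upper end together. It reverses, by 1–4 points, if non-owners complete 20 points more often. Overall it ranges from negligible to moderate. For Aim 1 the same mechanism applies but cannot be sized.

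Confidence is medium, because Figure 1 could show the same screen in both kinds of week. It should be fixed because the remedy is cheap and, unless ownership is recorded, the planned analysis cannot separate the tool from the make-up of the arms.

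**What to change.** - Ask the smartphone question of every participant in both ASA24 and Keenoa weeks, before that week's tool is offered. Record the answer and apply the same eligibility rule in both.
- State in the SAP that the Aim 1 and Aim 2 comparisons include smartphone owners only, in both arms. Non-owners may still give ASA24 records to the parent glucose study, as already planned.
- If Figure 1 already shows a common screen, revise the Methods paragraph to agree with it.

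**Cost.** One screening question in ASA24 weeks and one sentence defining the analysis set. With an assumed 5–20% of non-owners, 50 × .05 = 2.5 to 50 × .20 = 10 of 50 ASA24-week participants would leave the comparison. Within a six-week trial they may not be replaceable, so the ASA24 arm could be that much smaller.

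If 62.1% is a mixed rate and non-owners complete less often, the owners-only ASA24 rate is higher: .651 in the middle case and .701 in the upper case. With Keenoa held at 80%, two-sided power at 50 per group would fall from about 51% to 38% and 21% respectively. This is the power for the smaller difference between tools among owners, once the part due to arm composition is removed. It should be reflected when the sample size is revisited.

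### Aim 2's Keenoa response rate describes smartphone owners only, and no rate for all attendees is planned, so feasibility is incomplete for the whole cohort

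*Combined protocol and SAP*

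**What the plan says.** The Background and Rationale closes with the purpose: "we chose to assess the acceptability and feasibility of KeenoaTM in order to evaluate dietary habits in the Framingham Heart Study (FHS"). Aim 2 under Specific Aims uses a response rate "defined as the proportion of participants who complete all three days of diet assessments with energy intake >600 kcal", and the Aim 2 analysis compares, by chi-square, "the percentage who completed 3 days of dietary assessment with energy intake >600 kcal, from the two instruments".

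The tool is allocated by week. For Keenoa weeks the Methods section adds a smartphone question and, for people without one, this rule: "If not, individuals will not be eligible to participate in the trial, but they can still complete ASA24 dietary records". The stated reason for the ASA24 option is to keep their dietary data for the parent glucose study.

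The readable text describes no smartphone question in ASA24 weeks, no report of how many are screened out, and no analysis of everyone attending in a Keenoa week. Methods refers to Figure 1 for the full enrollment process, and that figure is not shown. Smartphone ownership in the cohort is not given.

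**The concern.** Lacking the required device is the most certain way for a smartphone tool to fail to produce a record. Under this plan that failure is never counted, because the person leaves the trial after the week's tool has been set. The Keenoa rate is then a rate among owners, while the ASA24 rate, on the readable text, is a rate among all comers.

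Two things are at stake. First, FHS examines owners and non-owners alike, and an owners-only rate overstates what Keenoa alone would deliver there. Second, a screen applied after allocation and in one arm only means that the groups compared are no longer those formed by the weekly randomization.

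**Working it through.** **Inputs.** From the Power calculation: ASA24, "we have had a response rate of 62.1% of participants completing 3 days of diet record using ASA24"; Keenoa, "We estimate that KeenoaTM would have an 80% response rate among our participants"; and "considering alpha=.05, and 80% power, the sample size required is 50 participants per group". Ownership *s* is not given, so 70% to 100% is assumed for illustration. The 80% is read as the owners' rate *K*.

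**The plan's own figure.** The usual two-group formula is n = [z(α/2)·√(2p̄(1−p̄)) + z(β)·√(p₁(1−p₁) + p₂(1−p₂))]² / (p₂−p₁)². With p₁ = 0.621, p₂ = 0.80 and p̄ = 0.7105 it gives 100 per group two-sided (79 one-sided). The stated 50 does not reproduce and has about 50% power two-sided. That is a separate matter, and the argument here does not depend on it.

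**Yield per attendee.**
- Keenoa as sole tool: *s* × 80%.
- Keenoa with ASA24 for non-owners: *s* × 80% + (1 − *s*) × 62.1%, assuming that non-owners respond to ASA24 at 62.1%.

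| Ownership *s* (assumed) | Keenoa only | Minus 62.1% | With fallback | Minus 62.1% |
|---|---|---|---|---|
| 100% | 80.0% | +17.9 | 80.0% | +17.9 |
| 95% | 76.0% | +13.9 | 79.1% | +17.0 |
| 90% | 72.0% | +9.9 | 78.2% | +16.1 |
| 85% | 68.0% | +5.9 | 77.3% | +15.2 |
| 75% | 60.0% | −2.1 | 75.5% | +13.4 |
| 70% | 56.0% | −6.1 | 74.6% | +12.5 |

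**Break-even for Keenoa as sole tool.** 62.1/80 = 77.6% ownership. With 50 per group and 31/50 on ASA24, the smallest significant Keenoa result is 40/50 (p = 0.047, uncorrected chi-square), and the break-even is then 31/40 = 77.5%.

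**Why the fallback behaves differently.** Let a_o and a_n be the ASA24 rates of owners and non-owners. Fallback yield is sK + (1−s)a_n and ASA24 for everyone is s·a_o + (1−s)a_n. The difference is s(K − a_o): non-owners cancel.

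**Effect of screening one arm only.** Suppose *s* = 80% and non-owners respond to ASA24 at 40% (both assumed). Then a_o = (0.621 − 0.2 × 0.40)/0.8 = 67.6%. Owners would exceed the all-comer 62.1% by 5.5 points with no difference between tools. The fallback yield would be 0.64 + 0.2 × 0.40 = 72.0%, a gain of 9.9 points rather than 17.9.

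**The case against.** The strongest reply is that the restriction is stated openly, that the formal aims concern participants, and that feasibility appears only in the rationale. An owners-only comparison also answers a legitimate question. With the screen in both arms it would rank the fallback strategy against ASA24 correctly, since the difference is s(K − a_o). This stands, and it limits the point: no passage proposes Keenoa as the sole tool, and the fallback is what the protocol allows.

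Three stronger readings may tempt a reader, and the documents do not support them.

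- **That Aim 2 would favour the tool with the lower yield.** This needs ownership below about 78% at the design rates, for which there is no evidence in the documents, and a Keenoa-only policy. Under fallback, a wrong ranking needs a_o > K > the all-comer ASA24 rate, which is a problem of unequal eligibility.
- **That feasibility is left unanswered.** It is answered for owners.
- **That screening both arms equally would make matters worse.** Against the Keenoa-only cohort difference, the overstatement is (1−s)K with the one-arm screen and (1−s)(K − a_o + a_n) with an equal screen. The second is larger only if a_n > a_o. With the values above it falls from 0.2 × 0.80 = 16.0 points to 0.2 × (0.80 − 0.676 + 0.40) = 10.5 points.

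Two cautions about the inputs also stand. The 80% might already be meant for all exam participants, in which case multiplying by ownership double-counts. The 62.1% is not stated to apply the >600 kcal criterion, so the break-even is approximate.

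The reply does not remove the gap itself. The readable plan has no Keenoa rate with all attendees in the denominator, although the purpose concerns FHS.

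**Conclusion.** The point holds as a gap in what Aim 2 can conclude, and it merits a change to the plan. The Keenoa rate will describe smartphone owners in Keenoa weeks, and any non-ownership makes it overstate Keenoa-only yield in the cohort. At 90% and 85% ownership the planned 17.9-point lead falls to 9.9 and 5.9 points, a loss of 8.0/17.9 = 45% and 12.0/17.9 = 67%. With the ASA24 fallback the loss is much smaller if non-owners respond at 62.1%.

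These sizes rest on an assumed ownership range, on reading 80% as the owners' rate, and on 62.1% as the ASA24 rate for the Aim 2 endpoint. The finding that the screen operates in one arm only is provisional, because Figure 1 is not shown.

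**What to change.** Pre-specify an Aim 2 analysis whose denominator is every exam attendee offered dietary assessment during the trial, grouped by the week's allocated tool. Report two rates for Keenoa weeks, each against all attendees in ASA24 weeks:

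- (a) completion on Keenoa, with non-owners counted as not completing on Keenoa;
- (b) completion under Keenoa with ASA24 fallback for non-owners.

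Report the number screened out, and base the feasibility conclusion for FHS on (a) and (b). Limit any owners-only conclusion to owners. If an owners-only comparison is kept, ask the smartphone question in ASA24 weeks too, unless Figure 1 already provides for it.

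Present these rates as estimates with confidence intervals. For (a), two-sided 80% power would need 173, 353 and 1,025 per group at 95%, 90% and 85% ownership, before any allowance for allocation by week, so a non-significant difference would say little.

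The cost is a simple log of attendees offered assessment and of their smartphone answers, SAP wording, and one extra tabulation. The text says that the question is asked in Keenoa weeks but not that the answers are kept, so the log should not be assumed to exist. The price in presentation is a less favourable Keenoa rate.
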